#### 7. PLANNED ANALYSIS

For End-Of-Text tables, the set of summary statistics is: N / Mean / Standard Deviation (STD) / Min / Median / Max.

For tables that are provided for endpoints with some extreme data, median, quartiles and percentiles are preferred to mean, standard deviation, minimum and maximum.

In general, means, medians, and percentiles are presented to one more decimal place than the raw data and STDs are presented to two more decimal places than the raw data. Minima and Maxima are presented to the same number of decimal places as the raw data.

Tabulations of frequencies for categorical data include all possible categories (even if there is no count in a category) and display the number of observations in a category as well as the percentage (%) relative to the number of subjects in the respective treatment group (unless otherwise specified, all subjects in the respective subject set whether they have non-missing values or not). Percentages are rounded to one decimal place, unless the denominator is smaller than 100 (in all treatment columns), in which case percentages are rounded to the nearest integer. The category missing will be displayed only if there are actually missing values.

If a table presents only categorical data, "[N (%)]" is displayed in the column header only.

Abbreviations (e.g. Wors.) or acronyms (e.g. PD) will not be displayed in tables and subject data listings without any explanation. They will be either spelled out or explained in footnotes.

If applicable, days will be converted to weeks, months or years as follows:

- weeks = days  $\div$  7
- months =  $12 \times \text{days} \div 365.25$
- years = days  $\div$  365.25

#### 7.1 DEMOGRAPHIC AND OTHER BASELINE CHARACTERISTICS

Only descriptive statistics are planned for this section of the report.

#### 7.2 CONCOMITANT DISEASES AND MEDICATION

Only descriptive statistics are planned for this section of the report.

Concomitant diseases will be coded similarly as AEs based on the most current MedDRA version. A summary of concomitant diseases will be provided by treatment group, system organ class (SOC), and preferred term (PT).

Concomitant therapies (CTs) will be coded according to WHO DD and classified by the Anatomical, Therapeutic, Chemical (ATC) classification system. The third ATC level will be

used to categorise CTs by therapy type. In situations where a medical product may be used for more than one equally important indication, there are often several classification alternatives. As appropriate, subjects receiving CTs with more than one possible ATC level-three category will be counted more than once. CTs will be summarised in two groups: CNS-active and non-CNS-active concomitant medications.

Summaries will also be provided for the following CTs of special interest: antipsychotics, benzodiazepines, anticholinergics, antiepileptics, and antidepressants, as defined in Table 10.7: 1.

#### 7.3 TREATMENT COMPLIANCE

Only descriptive statistics are planned for this section of the report. See Section 5.4 for definitions of treatment compliance. In addition, descriptive statistics of treatment adherence based on the AiCure data, as defined in Section 5.4, will also be reported.

#### 7.4 PRIMARY ENDPOINT ANALYSIS

#### 7.4.1 Primary analysis

In the primary analysis under the primary estimand, intercurrent events will be addressed using a strategy that differs depending upon the nature of the intercurrent event. For details please refer to Section 6.3 above (or Section 7 of the CTP). This primary analysis of the primary efficacy endpoint will be performed on the Randomized Set. With regard to the stratification factor, subjects will be analyzed according to the screening MCCB overall composite T-score stratum to which they correctly belong. Missing data resulting from the strategy (including both actual missing outcomes and excluded outcomes) will be handled using a mixed-effects model for repeated measures (MMRM) under the assumption of missing at random.

The primary endpoint is the change from baseline to Week 26 in overall composite T-score of the MCCB.

The primary analysis will be a restricted maximum likelihood (REML) based approach using a mixed-effects model for repeated measurements (MMRM) comparing the change from baseline in MCCB overall composite T-score at Week 26 between iclepertin 10 mg QD and placebo. The MMRM will includes the fixed categorical effects of treatment at each visit, a fixed categorical effect of the stratification factor using the screening MCCB overall composite T-score, and a fixed effect for the continuous covariate of baseline (i.e. baseline MCCB overall composite T-score) at each visit. Visit will be treated as the repeated measure with an unstructured covariance structure used to model the within-subject dependencies.

The statistical model will be as follows:

$$y_{ijkm} = \beta_j S_i + \tau_{jk} + \varphi_m + e_{ij},$$

where

[figure not shown]
$$(e_{i1}, \ldots, e_{iJ})' \sim N_J(\mathbf{0}, \Sigma),$$

[figure not shown]
and

[figure not shown]
```
y_{ijkm}= response variable for subject i in stratum m at visit j randomized to treatment k S_i= the baseline MCCB overall composite T-score of subject i,i=1,2,... \beta_j= coefficient of baseline effect at visit j,j=1,...,J \tau_{jk}= the effect of treatment k at vist j,k=1,2 \varphi_m= the effect of screening MCCB overall composite T-score stratum m for m=1,2, and \varphi_1\equiv 0 for stratum 1 of T-score <30 e_{ij}= the random error associated with jth visit of the ith subject. \Sigma= a J\times J unstructured covariance matrix
```

[figure not shown]
The Kenward-Roger approximation will be used to estimate the denominator degrees of freedom and adjust standard errors. Significance tests will be based on least-squares means, following the testing strategy described in CTP Section 7.1. The primary treatment comparison will be the contrast between iclepertin 10 mg QD and placebo at Week 26. Results of the MMRM (N, mean, SE and 95% CI per dose group and timepoint) will be presented in tables and displayed graphically.

[figure not shown]
Example SAS code for the primary analysis of MMRM is provided in Section 10.2.1. In the event of non-convergence, methods described in Section 10.2.2 will be attempted to overcome the issue.

[figure not shown]

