- If the patient is re-screened within 12 weeks of the original screening visit, all procedures **except** for the MCCB, SCoRS, VRFCAT and ToL must be performed.
- If the re-screening occurs more than 12 weeks from the initial screening, then all Visit 1 procedures must be repeated.

For all re-screened patients, the screening period will be again 35 days as per protocol. In case all eligibility criteria are met during these repeated screening procedures, the patient can be randomized on the newly planned Visit 2 date under the newly assigned patient number.

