7.2.3 Secondary endpoint analyses

For the two key secondary efficacy endpoints of change from baseline to Week 26 in SCoRS interviewer total score and adjusted total time T-score in VRFCAT, as well as the secondary efficacy endpoint of change from screening to Week 24 in PRECIS total score, the same strategy for handling the intercurrent events in the primary estimand analysis and a similar MMRM analysis used for the primary efficacy endpoint will be conducted to obtain the adjusted mean treatment effect between BI and placebo in terms of change from baseline to Week 26 (from screening to Week 24 for PRECIS total score). This MMRM model includes the discrete fixed effects of treatment at each visit, fixed categorical covariate of the stratification factor using the screening MCCB overall composite T-score, and continuous fixed effects for the corresponding baseline endpoint value at each visit. Visit will be treated as the repeated measure with an unstructured covariance structure to model the within-subject measurements. Subjects will be considered as a random effect. The primary treatment comparison is the contrast between treatments at Week 26 (Week 24 for PRECIS total score). For change from baseline to Week 26 in the T-score of the number of correct responses on ToL, an analysis of covariance (ANCOVA) model including treatment, stratification factor of screening MCCB overall composite T-score ($<30, \ge 30$), and baseline number of correct responses on ToL T-score will be fitted to the data.

Similar sensitivity and supplementary analyses as planned for the primary efficacy endpoint will also be conducted for the two key secondary efficacy endpoints.

Page 83 of 112

Proprietary confidential information © 2023 Boehringer Ingelheim International GmbH or one or more of its affiliated companies

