# 5. ENDPOINTS(S)

#### 5.1 PRIMARY ENDPOINT(S)

The primary endpoint is

• Change from baseline in MCCB overall composite T-score at Week 26.

MCCB assessments are planned to be performed at screening (Visit 1), baseline (Visit 2), Week 12 (Visit 6), and Week 26 (Visit 11/EOT) or any early end of treatment visit.

Any post-baseline MCCB assessments performed within 28 days of the previous assessment will be considered invalid because of potential practice effects and will be excluded prior to any subsequent data handling and therefore from the planned analyses (5).

The MCCB overall composite T-score will be derived from seven domain scores from a total of ten tests (see CTP Table 5.1: 1). A larger MCCB overall composite T-score indicates better cognition.

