#### 6.7 BASELINE, TIME WINDOWS AND CALCULATED VISITS

In general, baseline values are the measurements taken prior to the first administration of trial medication. For assessments of efficacy, and C-SSRS, baseline will be defined as the last available assessment performed at or before randomization (Visit 2), and no later than the day of the first administration of study medication. Assessments done at Visit 1 or Visit 1a can be used as baseline if Visit 2 assessment is not planned, not available, or invalid.

For MCCB, only the assessment performed at randomization (Visit 2), and no later than the day of the first administration of study medication will be used as the baseline. If no valid assessment is available at Visit 2 then baseline value will be missing; assessments performed at Visits 1 and 1a will not be used as baseline.

Tables in this section define the analysis visits and windows which will be used for the analyses of efficacy and safety endpoints. Actual study day will be calculated starting with the date of first administration of trial treatment as Day 1. Unscheduled assessments will be mapped to the analysis visits together with the scheduled assessments.

Inclusion of an assessment into mapping consideration will depend on its on-/off-treatment status and per specific estimand (i.e., off-treatment data will be included into mapping consideration only when the associated ICE is handled under the treatment policy approach). If more than one assessment falls into the same analysis visit window, the assessment

performed closest to the planned day will be selected for analyses. In case of a tie, the later assessment will be used.

Table 6.7: 1 Analysis visit windows for MCCB, VRFCAT, SCoRS,

Analysis Visit	Nominal Week	Planned Day	Actual Day Window
Baseline		1	≤1
Visit 6	Week 12	85	2 – 126
Visit 11	Week 26	183	≥127

Table 6.7: 2 Analysis visit windows for PRECIS,

Analysis Visit	Nominal Week	Planned Day	Actual Day Window
Baseline		1	≤1
Visit 7	Week 15	106	2 – 126
Visit 10	Week 24	169	≥127

Table 6.7: 3 Analysis visit windows for Tower of London,

Analysis Visit	Nominal Week	Planned Day	Actual Day Window
Baseline		1	≤1
Visit 11	Week 26	183	≥2
(for Tower of London,			

[figure not shown]

Table 6.7: 7 Analysis visit windows for clinical laboratory evaluations (on-treatment period)

Analysis Visit	Nominal Week	Planned Day	Actual Day Window
Baseline		1	≤1
Visit 2	Week 0 (post-baseline)	1	2 – 35
Visit 4	Week 6	43	36 – 77

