## 7.5 SECONDARY ENDPOINT ANALYSIS

# 7.5.1 Key secondary endpoint analysis

## 7.5.1.1 Primary analysis

For the two key secondary efficacy endpoints of change from baseline at Week 26 in SCoRS interviewer total score and VRFCAT adjusted total time T-score, the same strategy for handling the intercurrent events in the primary analysis under the primary estimand will be applied.

The primary analysis will be a restricted maximum likelihood (REML) based approach using the same primary analysis model of MMRM specified in Section 7.4.1, but with the baseline covariate replaced by the baseline of the corresponding key secondary endpoint.

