# 7.5.2 (Other) Secondary endpoint analysis

For the secondary efficacy endpoints of change from screening to Week 24 in PRECIS total score and change from baseline to Week 26 in Tower of London number of correct responses T-score, the same strategy for handling the intercurrent events in the primary analysis under the primary estimand will be applied.

For change from screening to Week 24 in PRECIS total score, the primary analysis will be a restricted maximum likelihood (REML) based approach using the same primary analysis model of MMRM specified in Section 7.4.1, but with the baseline covariate replaced by the screening PRECIS total score. The same subgroup analyses as planned for the primary efficacy endpoint in Section 7.4.3 will also be conducted for PRECIS total score.

For change from baseline to Week 26 in the T-score of number of correct responses on Tower of London, an analysis of covariance (ANCOVA) model including treatment, stratification factor of screening MCCB overall composite T-score (<30, ≥30), and baseline number of correct responses on Tower of London T-score will be fitted to the data.

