### 10.2 COMPUTATIONAL DETAILS OF THE MMRM ANALYSIS

### 10.2.1 Example SAS code for the primary analysis by MMRM:

[figure not shown]
```
PROC MIXED DATA=indata cl method=reml covtest;
    CLASS strata visit trt subject;
    MODEL ept = strata visit|trt base|visit / ddfm=kr s CL;
    REPEATED visit / subject= subject type=un r rcorr;
    LSMEANS visit*trt / pdiff=all om cl alpha=0.05 slice=visit;
RUN;
```

[figure not shown]

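### The primary, SCoRS, VRFCAT and ToL models leave out each instrument's continuous Visit 1 score; adding it is valid and cheap, and would cut residual variance by 0 to about 20%

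*SAP*

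**What the plan says.** The protocol Flow Chart schedules MCCB, SCoRS, VRFCAT and ToL at both Visit 1 and Visit 2. SAP 5.1 confirms this for the primary instrument: "MCCB assessments are planned to be performed at screening (Visit 1), baseline (Visit 2), Week 12 (Visit 6), and Week 26".

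The primary MMRM (SAP 7.4.1, Protocol 7.2.2) has treatment by visit, the Visit 2 MCCB composite as a continuous covariate by visit, and "a fixed categorical effect of the stratification factor using the screening MCCB overall composite T-score" with levels <30 and ≥30. The code in SAP 10.2.1 agrees: "MODEL ept = strata visit|trt base|visit / ddfm=kr s CL".

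For SCoRS and VRFCAT, SAP 7.5.1.1 reuses this model "but with the baseline covariate replaced by the baseline of the corresponding key secondary endpoint". Protocol 7.2.3 likewise lists "continuous fixed effects for the corresponding baseline endpoint value at each visit". For ToL, SAP 7.5.2 gives an ANCOVA with treatment and the MCCB stratum, ending "and baseline number of correct responses on Tower of London T-score will be fitted to the data".

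Under SAP 6.7 the Visit 1 score of an efficacy scale has only a fallback role: "Assessments done at Visit 1 or Visit 1a can be used as baseline if Visit 2 assessment is not planned, not available, or invalid". Even that is ruled out for MCCB; only a Visit 2 assessment can be the baseline.

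**The concern.** Where both pre-treatment scores exist, the earlier one is either discarded (SCoRS, VRFCAT, ToL) or reduced to two categories (MCCB). Two noisy measurements of a fairly stable trait usually predict a later value better than one, so the confidence intervals may be wider than the collected data allow. PRECIS is not affected, because it is first measured at Visit 1a.

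The primary has little to gain. The key secondaries have more. Under Protocol 7.1, with α₂ = 0.025 and γ = 0.2, both succeed if both one-sided p-values are below 0.025 × 1.2/2 = 0.015. Otherwise the smaller is tested at 0.025/2 = 0.0125. The phase II SCoRS effect in Protocol 7.5 was only about 0.2, against the 0.35 assumed.

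**Working it through.** **1. The plan's own figure.** From Protocol 7.5: effect 0.35, 220 evaluable per arm, one-sided 0.025. The noncentrality is 0.35 × √(220/2) = 3.671, so power is Φ(3.671 − 1.960) = 95.6%, matching Table 7.5:1. Effects of 0.31, 0.286, 0.268 and 0.25 give 90.0, 84.9, 80.1 and 74.4%, against the stated 90, 85, 80 and 75%. The enlarged total is 220/0.75 = 293 per arm, 586 in all.

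**2. Correlations.** The only correlation in the documents is 0.2, between endpoints. Assumed here: Visit 1–Visit 2 (r₁₂) from 0.7 to 0.9; Visit 2–Week 26 (r₂) at least 0.7 but no higher than r₁₂, since a 26-week gap should not correlate more strongly than about one month; Visit 1–Week 26 (r₁) from r₁₂·r₂, where Visit 1 adds nothing, up to r₂.

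**3. Residual-variance cut.** For SCoRS, VRFCAT and ToL, beyond the own baseline:

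cut = (r₁ − r₁₂r₂)² / [(1 − r₁₂²)(1 − r₂²)]

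At 0.85/0.80/0.75 this is (0.75 − 0.68)² / (0.2775 × 0.36) = 0.0049/0.0999 = 4.9%. With all three equal to r it becomes (r/(1+r))², for example (0.9/1.9)² = 22.4%. For MCCB the stratum already takes part of the gain, so the cut was computed beyond Visit 2 plus the split (cut-point at the mean or 0.5 SD below).

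| r₁₂ / r₂ / r₁ | MCCB | Own score |
|---|---|---|
| 0.85 / 0.80 / 0.68 | 0 | 0 |
| 0.85 / 0.80 / 0.72 | 1.1–1.2% | 1.6% |
| 0.85 / 0.80 / 0.75 | 3.4–3.6% | 4.9% |
| 0.9 / 0.7 / 0.7 | 3.8–4.0% | 5.1% |
| 0.7 / 0.7 / 0.7 | 9.7–10.7% | 17.0% |
| 0.8 / 0.8 / 0.8 | 13.1–14.1% | 19.8% |
| 0.9 / 0.9 / 0.9 | 17.8–18.6% | 22.4% |

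In patients, a 3.5% cut is worth 220/0.965 = 228 evaluable per arm, and a 4.9% cut 220/0.951 = 231.

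**4. Power through the gatekeeping procedure.** This used 2,000,000 simulated trials with 220 per arm, correlation 0.2 and γ = 0.2. Scenario 3 without any cut gave 95.6/12.7/78.9% for MCCB/SCoRS/VRFCAT and 79.9% for the primary plus at least one key secondary. Table 7.5:1 has 95.6/12.6/78.6% and 79.6%. Effects were then divided by √(1 − cut).

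| Endpoint (effect) | As planned | 3.5% MCCB, 5% own | 5% MCCB, 10% own |
|---|---|---|---|
| Primary (0.35) | 95.6% | 96.2% | 96.5% |
| VRFCAT (0.30, Scenario 3) | 78.9% | 81.3% | 83.4% |
| VRFCAT (0.25, Scenario 4) | 63.0% | 65.7% | 68.3% |
| SCoRS (0.20, VRFCAT 0.30) | 45.4% | 47.7% | 50.1% |

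**5. Validity and cost.** In complete-data ANCOVA simulations with 440 patients (4,000 null trials), one-sided rejection was 2.1–2.7% with or without the covariate (nominal 2.5%). The variance of the treatment estimate was multiplied by 0.966 at 0.85/0.80/0.75, and by 1.002 at 0.85/0.80/0.68, where Visit 1 is useless.

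**The case against.** The strongest objection is that nothing is wrong with the plan. It adjusts for the stratum and a continuous baseline by visit, protocol and SAP agree, and an extra covariate of unknown value is a preference. It is true that this is not an error.

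The documents also suggest that Visit 1 is the less standardised measurement:

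- The 8-hour restriction on sedating drugs before MCCB names Visit 2 and later assessments (Protocol 4.2.2.1), and anticholinergics may be reduced during screening.
- The 60-minute time-of-day rule is tied to Visit 2 (Protocol 6.2.1).
- Study-partner input to SCoRS is required at least at Visit 2 and end of treatment (Flow Chart footnote 20), so Visit 1 may lack it.
- When a patient "is re-screened within 12 weeks of the original screening visit, all procedures" apart from these four instruments are repeated, so some Visit 1 scores will be older.

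These points stand and push the likely gain towards the low end. A 10% own-score cut at r₁₂ = 0.85 and r₂ = 0.80 needs r₁ = 0.68 + √(0.10 × 0.0999) = 0.78, close to equality with Visit 2. One feature runs the other way: under SAP 10.1 a Visit 2 MCCB composite may rest on four domains, while Visit 1 needs five.

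The power figures treat the protocol's standardised effects as being on the planned model's residual SD, which the documents do not state. If 5.8 is instead the SD of raw change, the planned adjustment already lifts primary power to about 97.2% (assuming a baseline correlation of 0.8 and equal variances), and a 3.5% cut adds about 0.4 points. The validity check was also a complete-data ANCOVA, not the MMRM with its expected missing data.

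These points limit the size of the benefit. They do not remove it, because the stated range starts at zero and the possible loss is about 0.2% of variance.

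**Conclusion.** The point holds as a recommended efficiency step. The models shown omit a pre-treatment predictor that is already collected, and adding it leaves the estimand, bias and type I error unchanged. Under the assumed correlations the cut in residual variance is 0–19% for MCCB and 0–22% for the other three instruments. Low single figures are more plausible than the top of the range, given how Visit 1 is conducted.

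The practical value lies with the key secondaries: about two to three points of power at a 5% cut and about five at 10%. The primary hardly moves. SCoRS at an effect of 0.20 stays underpowered either way. Some SAP subsections are not in the public text, so this concerns only the models that are shown.

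**What to change.** Before unblinding, keep the stratum and the Visit 2 baseline in every model. In the primary MMRM add the continuous Visit 1 MCCB T-score by visit, by appending `scr|visit` to the MODEL statement. For SCoRS and VRFCAT add the instrument's own Visit 1 score by visit; for ToL add it to the ANCOVA. Prespecify three covariate rules:

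1. When a Visit 1 score already serves as the baseline under SAP 6.7, set it to missing as a covariate so that it does not enter twice. This cannot occur for MCCB.
2. Replace missing Visit 1 scores by the overall mean across arms and add a missingness indicator. Otherwise PROC MIXED drops those patients, and losing a share m of them cancels a gain of about m. Visit 1 MCCB is mandatory (exclusion criterion 25); the other three scores are not.
3. For patients re-screened within 12 weeks, link the Visit 1 scores held under the earlier patient number.

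Record the change in SAP section 4, because the models are also written in Protocol 7.2.2 and 7.2.3, and apply it in the planned pooled analyses of the three trials. The cost is one or two parameters per visit in each model, the short rule above and coordination with the two parallel trials. No new data or patients are needed.

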## 7.5 SECONDARY ENDPOINT ANALYSIS

# 7.5.1 Key secondary endpoint analysis

## 7.5.1.1 Primary analysis

For the two key secondary efficacy endpoints of change from baseline at Week 26 in SCoRS interviewer total score and VRFCAT adjusted total time T-score, the same strategy for handling the intercurrent events in the primary analysis under the primary estimand will be applied.

The primary analysis will be a restricted maximum likelihood (REML) based approach using the same primary analysis model of MMRM specified in Section 7.4.1, but with the baseline covariate replaced by the baseline of the corresponding key secondary endpoint.

# 7.5.2 (Other) Secondary endpoint analysis

For the secondary efficacy endpoints of change from screening to Week 24 in PRECIS total score and change from baseline to Week 26 in Tower of London number of correct responses T-score, the same strategy for handling the intercurrent events in the primary analysis under the primary estimand will be applied.

For change from screening to Week 24 in PRECIS total score, the primary analysis will be a restricted maximum likelihood (REML) based approach using the same primary analysis model of MMRM specified in Section 7.4.1, but with the baseline covariate replaced by the screening PRECIS total score. The same subgroup analyses as planned for the primary efficacy endpoint in Section 7.4.3 will also be conducted for PRECIS total score.

For change from baseline to Week 26 in the T-score of number of correct responses on Tower of London, an analysis of covariance (ANCOVA) model including treatment, stratification factor of screening MCCB overall composite T-score (<30, ≥30), and baseline number of correct responses on Tower of London T-score will be fitted to the data.

